9.4. Subject Status and Classification

Table 9-1 describes subject status/classification and associated forms.

Table 9-1: Subject Status and Classification

Classification	Description
Screen Failure	A subject who signs an ICF but does not meet clinical eligibility criteria and/or is not treated or attempted to be treated with a WATCHMAN FLX Pro device is considered a screen failure. Screen failure subjects do not count towards the enrollment ceiling and will not be used for the primary analyses. Screen failure subjects should exit from the study immediately upon determining ineligibility. The original signed ICF must be maintained in the center's subject file.
Attempt	A subject who signs an ICF, meets eligibility criteria, and has had a WATCHMAN Access Sheath inserted to implant the device, but does not receive a WATCHMAN FLX Pro device will be classified as "Attempt." Subjects in which a WATCHMAN FLX Pro device is inserted into a different anatomical location/structure (not within the LAA) will also be classified as "Attempt." Attempt subjects will be followed for 12 months from the time of the implant attempt and adverse events will be collected. Attempt subjects will not undergo protocol required imaging at 45 days or 12 months. Attempt subjects are considered enrolled and therefore count towards the enrollment ceiling. Attempt subjects will be used for analyses of the ITT analyzed endpoints. The original signed ICF must be maintained in the center's study file and the following forms must be completed. 
 • eCRFs in the Baseline and Implant folders • Follow-up Visit Form(s), except LAA imaging • Adverse Event forms and/or Device Deficiency forms for any reportable adverse event that occurs after signing the ICF • End of Study form for withdrawal The date of withdrawal should be indicated in the End of Study form as the point of subject withdrawal.
Implant	A subject who signs an ICF, meets eligibility criteria, and is implanted with the WATCHMAN FLX Pro device will be classified as "Implant." Implanted subjects are those where the device has been deployed and implanted in the correct anatomical position (LAA). These enrolled subjects are followed in accordance with the follow-up schedule and data will be included in all study analyses. All applicable case report forms per the protocol must be completed. The original signed ICF and any relevant documentation must be maintained in the center's study file.

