A	Age 75 years or older	2																																							
D	Diabetes Mellitus	1	Treatment with oral hypoglycemic drugs and/or insulin or fasting blood glucose >125 mg/dl (7 mmol/L)																																						
S	Stroke	2	Previous stroke, TIA, or thromboembolism																																						
V	Vascular Disease	1	Angiographically significant coronary artery disease (CAD), previous myocardial infarction (MI), peripheral artery disease (PAD), or aortic plaque																																						
A	Age 65-74 years	1																																							
Sc	Sex Category (female)	1																																							
Maximum Score		9																																							

	
^aFor further detail, please reference Table 8 from the 2020 ESC Guidelines for the diagnosis and management of atrial fibrillation developed in collaboration with the European Association for Cardio-Thoracic Surgery (EACTS); European Heart Journal (2020) 42, 373-498 doi:10.1093/eurheartj/ehaa612
 
^bLV dysfunction: Severe <35%; Moderate 35-40%; Mild: 41-49%; Normal >50%.

Correct Anatomical Position	Refers to the deployment of the WATCHMAN FLX Pro implant within the Left Atrial Appendage. It does not imply or require proper positioning within the LAA nor does it exclude implant embolization after final implant release.

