DEATH	
Cardiovascular Death Any one of the following criteria is met.
 
 • Death due to proximate cardiac cause (e.g., myocardial infarction, cardiac tamponade, worsening heart failure, endocarditis, etc.) • Death caused by noncoronary, non-CNS vascular conditions such as pulmonary embolism, ruptured aortic aneurysm, dissecting aneurysm, or other vascular disease • Death from vascular CNS causes 
 ◦ Hemorrhagic stroke ◦ Ischemic stroke • All-cause mortality during the index procedure, any procedure-related death within 30 days after the index procedure or during postoperative hospitalization for the index procedure (if >30 days), including those related to a complication of the procedure or treatment for a complication of the procedure • Unexplained death (see below) 
Non-cardiovascular Death
 
 • Any death in which the primary cause of death is clearly related to another condition (e.g., trauma, cancer, suicide) 
Unexplained Death
 
 • Sudden or unwitnessed death defined as a non-traumatic, unexpected fatal event occurring within one hour of the onset of symptoms in an apparently healthy subject. If death is not witnessed, the definition applies when the victim was in good health 24 hours before the event. • Death of unknown causes
DEVICE DEFICIENCY	Inadequacy of a medical device with respect to its identity, quality, durability, reliability, safety, or performance. 
Note 1: Device deficiencies include malfunctions, use errors, and inadequate labeling.

DEVICE EMBOLIZATION	Defined as movement of the device during or after deployment such that it dislodges and entirely leaves the LAA or completely loses contact with the LAA.
DEVICE MIGRATION	Defined as shifting of the implant within the LAA to create an inadequate seal where the gap is greater than 5mm at 45 days or later and the physician must intervene (e.g., adjust patient's anticoagulant regimen).
DEVICE RELATED THROMBUS	Thrombus formation on the atrial facing side of the device, possibly resulting in the need for anticoagulation and/or hospitalization.
DEVICE SUCCESS	Defined as implantation of a WATCHMAN FLX device in the correct anatomical position and without in-hospital mortality

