4.1.2 Attempt

A subject who signs an ICF, meets eligibility criteria, and has had a WATCHMAN Access Sheath inserted to implant the device, but does not receive a WATCHMAN FLX Pro device will be classified as “Attempt.” Attempt subjects will be used for analyses of the ITT analyzed endpoints.

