4.2 Analysis Sets

Endpoints will be analyzed on an intention-to-treat (ITT) basis and an implanted basis. For ITT analyses, all subjects who sign the IEC-approved study ICF and are enrolled in the study will be included in the analysis, whether or not a study device was implanted. For implanted analyses, ITT subjects who had the study device implanted in the correct position during the index procedure will be included in the analysis.

- Primary analysis subset

The initial 500 patients enrolled in HEAL-LAA will be included in the primary analysis subset. Primary endpoints will be assessed on an intention-to-treat (ITT) basis and an implanted basis. The ITT analysis set includes all subjects who sign an Informed Consent Form, meet all clinical inclusion and no clinical exclusion criteria, and the WATCHMAN FLX Pro device has been used for treatment and/or attempted to be used for treatment. The hypothesis tests (PGs) are only based on the Primary Analysis Subset.

- Access system subset

The initial 300 TruSteer Attempt or TruSteer Implant subjects will be included in access system subset.

- Diversity Subset

Non-Caucasian subjects will be included in the diversity subset. There is no formal statistical hypothesis for this subset.

- Full enrollment set

All enrolled subjects will be included in this subset. There is no formal statistical hypothesis for this subset.

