5.1 Other Endpoints/Measurements

No statistical hypothesis test will be conducted for other endpoints/measurements. The variables of interest will be summarized using descriptive statistics for continuous variables (e.g., mean, standard deviation, n, minimum, maximum) and frequency tables or proportions for discrete variables. The Kaplan-Meier product-limit method will be used to estimate rates for time-to-event endpoints. Adverse event and serious adverse event (SAE) rates will be reported.

Additional endpoints will include the following:

1. CEC-adjudicated:

- Device Success: Defined as implantation of a WATCHMAN FLX Pro device without in-hospital mortality.
- All-cause mortality: Cardiovascular/unknown death and non-cardiovascular death
- All Stroke: Disabling and non-disabling stroke; ischemic and hemorrhagic stroke
- Bleeding: International Society on Thrombosis and Haemostasis (ISTH) major and non-major clinically significant
 - Procedural bleeding and non-procedural bleeding
- Pericardial effusion/tamponade requiring pericardiocentesis or surgery
- Systemic embolism

2. Site reported:

- Device-related thrombus

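### SAP 5.1, 4.1.2 and 4.1.3 omit the protocol's within-the-LAA condition, so a device released outside the LAA would count as an Implant and a device success; SAP 4.2 also departs from the SAP's own term

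*SAP*

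**What the plan says.** **Device success.** Protocol Table 24-2: "Defined as implantation of a WATCHMAN FLX device in the correct anatomical position and without in-hospital mortality". SAP 5.1: "Defined as implantation of a WATCHMAN FLX Pro device without in-hospital mortality". The SAP has no other definition of device success.

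**Attempt.** Protocol Table 9-1 has two routes into this class. One is that the access sheath went in but no device was received. The other reads "Subjects in which a WATCHMAN FLX Pro device is inserted into a different anatomical location/structure (not within the LAA) will also be classified as" Attempt. SAP 4.1.2 keeps only the first route: a subject who had the sheath inserted "but does not receive a WATCHMAN FLX Pro device will be classified as" Attempt.

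**Implant.** Protocol Table 9-1: "Implanted subjects are those where the device has been deployed and implanted in the correct anatomical position (LAA"). SAP 4.1.3 asks only that the device was implanted, and puts these subjects into every study analysis.

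**What the position term means.** Protocol Table 24-2 defines *correct anatomical position* as deployment inside the LAA and adds: "It does not imply or require proper positioning within the LAA nor does it exclude implant embolization after final implant release".

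**Implanted analysis set.** SAP section 1 uses *correct anatomical position* for this set and names it as the set for the leak endpoint. SAP 3.3 uses the same term for implant success in the Access System subset. SAP 4.2 instead says "ITT subjects who had the study device implanted in the correct position during the index procedure will be included in the analysis", and the SAP does not define *correct position*.

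**Leak denominator.** SAP 3.1.3 counts primary-subset subjects with a core-lab 45-day TEE. It mentions neither the implanted set nor position.

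**The concern.** The same condition is missing from three SAP clauses that a programmer would use to derive subject class and device success. Under the protocol, a device left outside the LAA is a failed attempt. Under those SAP clauses it is an implanted, successful case. The study design statement in both documents names device success, with safety, as what the trial evaluates, and protocol section 7.3 says it will be reported for all enrolled subjects. The reported rate should therefore follow the protocol definition.

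The wording of SAP 4.2 is a second, smaller matter. The protocol defined its position term carefully so that it would not be taken to mean well seated. Dropping the word *anatomical* breaks the link to that definition in the section where analysis sets are formally described.

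**Working it through.** **1. Do any planned figures depend on the wording?** The leak endpoint is the tested endpoint that uses the implanted set. Inputs from protocol 11.1.1.2 and SAP 3.1.2: expected rate 2%, performance goal 5%, one-sided alpha 0.025, 400 evaluable, 20% attrition, 500 enrolled, power above 85%.

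Power of the one-sample z-test, with the null standard error in the critical value:

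Φ[(0.05 − 0.02 − 1.96 × √(0.05 × 0.95/400)) / √(0.02 × 0.98/400)]
= Φ[(0.03 − 1.96 × 0.01090)/0.00700] = Φ(1.235) = 89.1%

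This agrees with the stated figure of above 85%. Enrolment: 400/(1 − 0.20) = 500, as stated. Neither calculation takes subject class or device position as an input.

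**2. How each case is classified.** All subjects below are assumed to be discharged alive.

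| Case | Protocol Tables 9-1 and 24-2 | SAP 4.1.2, 4.1.3 and 5.1 |
|---|---|---|
| Within the LAA, well seated | Implant, success | Implant, success |
| Within the LAA, poorly seated | Implant, success | Implant, success |
| Within the LAA, embolises after final release | Implant, success | Implant, success |
| Released outside the LAA | **Attempt, not success** | **Implant, success** |
| Sheath inserted, no device received | Attempt, not success | Attempt, not success |

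Only the fourth row differs. In that row the SAP also disagrees with itself. Section 4.1.3 sends the subject into every analysis, while section 1, and 4.2 on either reading, keeps the subject out of the implanted set.

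**3. Size for device success.** Each wrong-site case moves one subject from non-success to success. With all enrolled subjects as the denominator (protocol 7.3), the change is k/N.

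| Wrong-site cases k (assumed) | N = 500 | N = 1000 |
|---|---|---|
| 1 | 1/500 = 0.2 points | 1/1000 = 0.1 points |
| 2 | 0.4 points | 0.2 points |
| 5 | 1.0 points | 0.5 points |

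The documents give no wrong-site rate, so k is an assumption.

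**4. Poorly seated devices in the leak analysis.** Take a device within the LAA but poorly seated, with a core-lab 45-day TEE:

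- SAP section 1: in the implanted set, because *correct anatomical position* does not require good seating.
- SAP 4.1.3: an Implant, and so in every analysis.
- SAP 3.1.3: in the denominator, because the TEE exists; in the numerator if the leak exceeds 5 mm.
- SAP 4.2: in, if *correct position* is shorthand for the protocol term; out only if it means well seated.

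Three of the four sections keep the subject, and the fourth removes the subject only on one of two readings.

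**The case against.** The strongest case for leaving the text alone is that the protocol already settles subject class in Table 9-1, the SAP says it is based on that protocol, and device success carries no hypothesis test. The only tested implant-success endpoint, for the Access System subset in SAP 3.3, keeps the position condition. No wrong-site case is forecast anywhere. All of this is correct, and it limits the consequence. It does not remove the conflict, because SAP 5.1 states its own definition and that definition classifies a wrong-site device differently from the protocol.

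A reader might go further in three ways, none of which the documents support:

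- *That poorly seated devices, those most likely to leak, drop out of the primary efficacy analysis and make a false pass more likely.* This needs SAP 4.2 to be read as well seated and then to override section 1, 3.1.3 and 4.1.3. The more natural reading is shorthand. Any figure for a raised false-pass chance would also need invented counts of poorly seated and leaking devices.
- *That the wording changes all favour the device.* The looser success definition does. The looser Implant class does not clearly do so, since it would bring wrong-site devices into analyses from which the protocol keeps them out.
- *That listing device success as CEC-adjudicated is an error.* Protocol 19.2 does not name it, but it lists all-cause mortality, which is the clinical event within device success, and allows other events at the sponsor's discretion. The listing does not contradict that.

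**Conclusion.** The point holds as a conflict of definitions between SAP and protocol. SAP 5.1, 4.1.2 and 4.1.3 omit the condition that the device be within the LAA, and the result is a wrong class and a wrong success status for one type of case: a device released outside the LAA in a subject discharged alive. The size is 0.2 percentage points per case in 500 subjects and 0.1 in 1000, on an untested descriptive endpoint. This rests on all enrolled subjects forming the denominator and on an unknown, probably small, number of cases. Sample size, power and alpha are unaffected.

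The wording in SAP 4.2 is an inconsistency within the SAP. It should be aligned, but it does not show that the leak analysis loses subjects. This is a minor point, worth correcting because the correction is so cheap.

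**What to change.** In the SAP:

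- **4.1.3, 4.2 and 5.1:** use *correct anatomical position (within the LAA, as defined in protocol Table 24-2)*.
- **4.1.2:** restore the rule that placement of a device outside the LAA makes the subject an Attempt.
- **3.1.3:** state that the leak denominator is the implanted set of the primary analysis subset with a core-lab 45-day TEE, so that it matches section 1.

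The cost is a SAP wording amendment, with no protocol change, no new data and no recalculation. It should be approved before the analyses are run, as SAP 5.6 provides, so that the choice of definition cannot appear to follow the results.

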5.2 Interim Analyses

There will be no formal interim analysis.

5.3 Subgroup Analyses

The following subgroups will be analyzed for the primary endpoints within the study:

- Sex (Female vs. Male)
- Age at time of consent (< 75 years vs. \geq 75 years)
- Race/ethnicity
- Stroke risk (CHA₂DS₂-VASc Score)
- Bleeding risk (HAS-BLED Score)

5.4 Multivariable Analyses

Univariate and multivariate modeling analyses will be performed to assess the effect of baseline covariates on the primary effectiveness and safety endpoints. Logistic regression

will be used to assess the effects of possible predictors on the primary effectiveness and safety endpoints.

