11.1.1.2. Sample Size

The sample size calculation for the primary efficacy endpoint of leaks is based on the following assumptions.

- Expected rate for WATCHMAN FLX Pro < 2% (based on historic studies of FLXibility and PINNACLE FLX)
- Testing margin = 3%
- PG = 5% = expected rate (2%) + testing margin (3%)
- 1-sided significance level (α) = 0.025
- Power (1 minus β) > 85%
- Number of evaluable subjects = 400
- Expected attrition rate = 20%

Primary Analysis Subset enrollment for the study = 500 subjects.

If the P value from the one-sample z-test is <0.025, the rate of the primary efficacy endpoint for the WATCHMAN FLX Pro Primary Analysis Subset will be concluded to meet the PG. This corresponds to the one-sided upper 97.5% confidence bound on the observed rate of the primary efficacy endpoint being less than the PG.

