3.1.2 Sample Size

The sample size was estimated based on the following assumptions:

- Expected rate for WATCHMAN FLX Pro $< 2\%$ (based on historic studies of FLXibility and PINNACLE FLX)
- Testing margin = 3%
- PG = 5% = expected rate (2%) + testing margin (3%)
- 1-sided significance level (α) = 0.025
- Power (1 minus β) $> 85\%$

- Number of evaluable subjects = 400
- Expected attrition rate = 20%

Given the above assumptions, 500 subjects of primary analysis subset will be required.

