3.1.3 Statistical Methods

The primary analysis subset with a completed 45-day follow-up TEE will be eligible for inclusion in this endpoint analysis. The primary analysis subset with core lab-completed 45-day TEE will be included in the denominator for the primary effectiveness event rate. The primary analysis subset with core lab-completed 45-day TEE and demonstrated leak $>5\text{mm}$ will be included in the numerator. A one-sample z-test will be used to test the assumption that the rate of leak $>5\text{ mm}$ at 45-day post-implant TEE is $\geq 5\%$. The null hypothesis will be rejected if the resulting p-value is less than 0.025.

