5 ADDITIONAL DATA ANALYSES

The additional data analysis in this section will be applied to all four analysis subsets: primary analysis subset, access system subset, diversity subset, and full enrollment set.

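### SAP 5.4 plans multivariable logistic regression for leak >5 mm on about 8 expected events or fewer, with no rare-event method named, so these models may often not be estimable

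*SAP*

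**What the plan says.** SAP 5.4 commits to the models: "Univariate and multivariate modeling analyses will be performed to assess the effect of baseline covariates on the primary effectiveness and safety endpoints". The next sentence names logistic regression for both endpoints. The section gives no covariate list, selection rule or minimum number of events, and mentions no penalised or exact method. Protocol 11.3.5 leaves the detail to the SAP, so it appears in neither document.

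The opening sentence of SAP section 5 says that its analyses "will be applied to all four analysis subsets": primary analysis, access system, diversity and full enrollment.

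For the leak endpoint, Protocol 11.1.1.2 and SAP 3.1.2 plan an expected rate below 2% and a performance goal of 5%. SAP 3.1.2 adds "Number of evaluable subjects = 400" and, after 20% attrition, "500 subjects of primary analysis subset will be required". SAP 3.3.2 sets the access system subset at 300, and SAP section 2 puts total enrollment at about 1000. Neither document states an expected number of leaks.

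**The concern.** A sample size chosen to show that an event is rare leaves few events for a predictor model. When every leak falls at one level of a covariate, or the covariates together separate leaks from non-leaks, the maximum-likelihood log odds ratio has no finite value. Software then prints a very large number with a meaningless interval.

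At stake is the predictor analysis for the primary efficacy endpoint. If separation appears when the model is run, the analyst must drop covariates or change method after seeing the data. Under SAP 5.6, a change of method made after the analysis has to be reported with a reason in the clinical study report.

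**Working it through.** **The plan's own figure.** One-sample z-test, 2% against 5%, one-sided 0.025, 400 evaluable:

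Power = Φ((0.03 − 1.96 × √(0.05 × 0.95/400)) / √(0.02 × 0.98/400)) = Φ((0.03 − 0.02136)/0.007) = Φ(1.23) = 89.1%.

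This meets the stated power of more than 85%, and 400/0.80 = 500 reproduces the enrollment. The inputs are consistent.

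**Expected leaks = evaluable subjects × rate**

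- Primary analysis subset: 400 × 0.02 = 8 (binomial 95% range 3 to 14). Because the rate is stated as below 2%, 8 is the expected count at the planning ceiling. At 1% it is 4. At 0.5% it is 2, with a 13% chance of none.
- Access system subset, assuming 20% attrition: 300 × 0.80 × 0.02 = 4.8.
- Full enrollment set, assuming 20% attrition: 1000 × 0.80 × 0.02 = 16.
- Diversity subset: no size is given, so no count can be derived.

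Rates of 1% and 0.5% are assumptions. They are plausible because Protocol 4.1.2 reports 100% effective closure (flow ≤5 mm) with the predecessor device, although at 12 months rather than 45 days.

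**Events per covariate.** SAP 5.3 lists five subgroup factors. Taking five covariates as an assumption, 8/5 = 1.6 leaks per covariate. For safety, 485 × 0.14 = 67.9 events, and 67.9/5 = 13.6 per covariate.

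**Simulated maximum-likelihood fits.** Two assumed covariate sets were used:

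- Mixed set: three binary factors with prevalences 40%, 55% and 15%, and two standard-normal scores. One binary factor has a true odds ratio of 2.
- Binary set: five binary factors.

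The table gives the share of data sets with no events or at least one divergent coefficient. The single-factor column is for a factor present in 40% of subjects.

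| Evaluable | Leak rate | Expected leaks | Five covariates, mixed | Five covariates, binary | One factor |
|---|---|---|---|---|---|
| 400 | 2% | 8 | 34% | 31% | 4% |
| 400 | 1% | 4 | 67% | 69% | 26% |
| 400 | 0.5% | 2 | 89% | not run | 60% |
| 240 | 2% | 4.8 | not run | 61% | not run |
| 800 | 2% | 16 | 9-10% | not run | 0% |

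A cruder count agrees. With five binary covariates of prevalence 20-50% and no true effects, at least one covariate level holds no leak in 33% of data sets at 400 and 62% at 240 (2% rate).

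The single-factor figure depends on prevalence. For a factor present in 15% of 400 subjects (60) and unrelated to leak, the chance of no leak among them at 2% is 0.98^60 = 0.30.

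**Bias and precision where the fit converges** (400 subjects, 2%, five mixed covariates). The mean log odds ratio was 0.71 against a true 0.69, and the median standard error was 0.75. The 95% limits therefore differ by a factor of exp(2 × 1.96 × 0.75) ≈ 19. The mean leaves out the divergent fits.

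**Firth fits on the same kind of data** (400 subjects, 2%). All were estimable, against about two thirds with maximum likelihood. The mean log odds ratio was 0.68 against 0.69, with a standard deviation of 0.74. At 1%, 1.4% failed, in line with the 0.99^400 = 1.8% chance of no leak at all.

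**Safety model** (485 subjects, 14%, five covariates): no estimation failures.

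**The case against.** The strongest reply is that this is under-specification and not a wrong method. SAP 5.4 says only logistic regression. Firth regression is a form of it and is not excluded, and neither document fixes the number of covariates, which drives the failure rate. The section also plans univariate models, which fail far less often for a common factor, and the full enrollment set gives about twice the events. No hypothesis test or success criterion uses these models: the leak conclusion rests on the z-test in SAP 3.1. SAP 5.6 allows an amendment before analysis.

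All of this stands, and it makes the point a minor one. It does not remove it. The SAP says that multivariate models will be run for leak in every subset, and plain logistic regression is normally read as unpenalised maximum likelihood.

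A reader might go further and infer that the leak odds ratios will be biased or not estimable. The figures do not support that. At the planning rate about two thirds of five-covariate fits were estimable, and those showed little bias. A reader might also want a fixed rule of 10 leaks per parameter. No document sets one. With about 16 leaks in the full enrollment set it would allow one parameter, and so rule out every multivariable leak model at the planning rate.

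**Conclusion.** The concern holds as a risk of unstable or non-estimable multivariable leak models. The expected count of about 8 or fewer in the primary analysis subset follows directly from the plan. The counts of about 5 and 16 elsewhere assume the same 20% attrition. With five assumed covariates, failure is expected in roughly a third of data sets at 400 subjects and 2%. It rises to about 60% at 240 subjects, and to about two thirds at 400 subjects if the true rate is 1%. The main defect of fits that do converge at 2% is imprecision. The weakness is concentrated in multivariable models in the smaller subsets; about a tenth of five-covariate fits fail at 800 evaluable subjects. The safety model and the primary leak test are sound on this point. This is an inexpensive improvement to a supporting analysis.

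**What to change.** In SAP 5.4:

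- State that all leak models will use Firth penalised-likelihood logistic regression with profile-likelihood intervals.
- Make univariable models the main predictor analysis for leak.
- Label any multivariable leak model exploratory, and name its few covariates in advance.
- Keep the planned logistic model for the safety endpoint.

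The cost is a short SAP amendment before analysis and the FIRTH option in SAS. Firth gives finite estimates but does not add information: the standard deviation of the log odds ratio stays at about 0.75 with 400 subjects at 2%. Adjusted leak results will be limited, and with no leaks in a subset no model can be fitted.
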